Research assessments are noninvasive and should add no substantial risk. The major disadvantages are the time taken to complete them and potential for a breach of confidentiality. Completion of the assessment interviews and surveys may cause some mild anxiety or embarrassment to some participants. Past experiences of the PI and study team indicate that the measures are acceptable to participants. Careful efforts aimed at maintaining confidentiality will be made (as described below).

There is a chance that participants' eating concerns and overweight may fail to improve or may worsen during the study. Participants will be withdrawn from the study if their clinical condition deteriorates to a significant degree, and they will be provided with appropriate referrals.

11. Minimizing Risks: Describe the manner in which the above-mentioned risks will be minimized.

The study clinicians will be carefully trained and supervised by the PI. All study clinicians and study staff will have IRB and ethics training; because of their educational experience and training (e.g., in psychology), they can reasonably be expected to identify potential problems and to take appropriate action as medically indicated. The PI will be continuously available to the study clinicians to discuss any problems and to implement any needed interventions or offer appropriate referrals. The detailed assessments repeated during the course of treatment will allow for additional and ample opportunity to identify difficulties. In the event that a participant experiences undue distress, resources are available. If a study participant experiences any psychiatric symptoms or distress (e.g., depressive symptoms or suicidality) at any stage of study participation they will receive short-term treatment and support from the PI and study treatment team (which includes psychologists) and will be connected with a local emergency department and their physician or a therapist for ongoing care.

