Study participant safety will be monitored by the study team and reported to the PI at all visits and referrals will be provided if warranted and/or requested. If a study participant experiences any psychiatric symptoms or distress (e.g., depressive symptoms or suicidality) at any stage of study participation they will receive short-term treatment and support from the study treatment team (which includes psychologists) and will be connected to a local emergency department and their physician or therapist for ongoing care.

Other Potential Issues Relating to Stopping Rules for the Pilot RCT Include:

- 1) **New Information:** It is unlikely that any new information would become available during this trial that would necessitate stopping the trial. If new data become available, these will be evaluated.
- 2) **Limits of Assumptions:** It is possible that baseline differences between the treatment conditions, excessive attrition, and/or missing data could limit the value of data analysis. Baseline differences across treatment groups, if present, will be evaluated twice yearly and considered in relation to potential effects on the power to detect differences in the primary outcomes. If these effects were to develop and be sizeable, alterations to the randomization schedule would be considered. Any plans to alter the randomization scheme would be communicated to the NIH.
- 3) **Limits of Rules:** There are other situations that could occur that might warrant stopping the trial and/or including a section on the safety report entitled “Other situations that have occurred since the last safety report that warrant discussion” to allow for communication of concerns.

13. **Statistical Considerations:** Describe the statistical analyses that support the study design.

DATA ANALYSIS AND AIMS

Baseline demographic and clinical characteristics will be compared between treatment and control groups using chi-square tests for categorical variables (e.g., sex) and ANOVAs or Kruskal-Wallis tests for continuous variables (e.g., BMI z-score). Continuous variables will be examined for adherence to normality using probability plots and Kolmogorov-Smirnov tests. If normality is not satisfied and transformations do not achieve acceptable normality, alternative strategies (e.g., nonparametric) will be considered. Dropouts and completers will also be compared. Analyses will be intent-to-treat. Outcomes will be tested at the $\alpha=0.05$ threshold.

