Overall analysis strategy. Descriptive statistics will quantify change and mixed-effects models (106, 107) will compare treatments through post; 3-month follow-up will be exploratory. These models allow for different numbers of observations per participant, use all available data on each participant, account for clustered data observations, and are unaffected by data missing at random. A further advantage is the capacity to test and account for individual-difference contributions to treatment outcomes (108). This strategy provides flexibility in modeling the correlation structure of the data. In models for each outcome, we will include fixed effects of time and treatment and their interaction, and random subject-level effects. Because we cannot *a priori* predict the shape of the response over time, we will first treat time as categorical and then test for polynomial trends. We will consider different error structures (e.g., compound symmetry, autoregressive) and select the best-fitting structure based on information criteria. Data on all participants enrolled in the study will be used in mixed models. We will compare dropout patterns and if there are concerns of informative dropout and/or informative intermittent missing data, we will use pattern mixture models to perform sensitivity analyses to main analyses.

Primary Aims.

Primary Aim 1 is to **test** the efficacy of adolescent CBT relative to the active control condition at post-treatment on clinical outcomes, including: (a) reduction in binge/LOC eating frequency (evaluated by the QEWP), and (b) reduction in weight (evaluated by BMI z-score). Significant time-by-treatment effects with significantly less adolescent binge/LOC eating and significantly reduced weight in adolescent CBT relative to the control condition will be considered supportive of these aims. Parallel analyses will also assess binge/LOC frequency reduction using the EDE; because this interview is only administered at baseline and post, this analysis will, by definition, occur among completers. Adolescent CBT is hypothesized to yield reduced binge/LOC eating frequency and weight reduction (i.e., weight loss or less excess weight gain) compared to the control group.

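### Adolescents who deteriorate leave the study with no planned outcome collection, so values tied to both primary outcomes are lost under an intent-to-treat label

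*Combined protocol and SAP*

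**What the plan says.** Section I, item 10 (Risks) warns: "There is a chance that participants' eating concerns and overweight may fail to improve or may worsen during the study". It continues: "Participants will be withdrawn from the study if their clinical condition deteriorates to a significant degree", with referrals provided. The rule ends participation in the study, not only study treatment. It sets no threshold, names no one who decides, and makes no provision for assessments afterwards. No other section makes that provision either.

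Item 13 (Statistical Considerations) says: "Analyses will be intent-to-treat". Its overall analysis strategy adds: "Data on all participants enrolled in the study will be used in mixed models". It recommends mixed models because they "account for clustered data observations, and are unaffected by data missing at random". Dropout patterns will be compared. A further step applies only "if there are concerns of informative dropout and/or informative intermittent missing data": in that case, pattern mixture models would serve as a sensitivity analysis.

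The primary outcomes are QEWP binge/LOC frequency and BMI z-score at post-treatment. Table 2 schedules both at baseline, Months 1 to 3, post and follow-up. The EDE interview is scheduled only at baseline and post, and item 13 states that its parallel analysis is among completers. In item 4, CBT participants have weekly clinician sessions, while control participants receive weekly mailings and monthly assessments.

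**The concern.** An intent-to-treat comparison at post-treatment needs post-treatment outcomes from everyone randomised, including those who did badly. The withdrawal rule removes some participants because they did badly, on grounds that overlap what is being measured. What the analysis then knows about them depends on whether the worsening was captured before they left. No passage requires a QEWP or weight at the time of the decision.

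The design gives the two arms different chances of capture. A CBT clinician can see worsening in any week and act before the next monthly QEWP. In control, worsening would more often come to light at a scheduled assessment, where it is recorded. The share of unrecorded deterioration could therefore differ by arm. The trial is meant to supply effect sizes for later definitive studies, so a bias here would carry forward.

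**Working it through.** **1. The plan's own figure.** Two-sided alpha 0.05, 25 per arm, d = 0.8, two-sample t: noncentrality = 0.8 × √(25/2) = 2.83, power 79.1% (normal approximation 80.7%). With 20 per arm and d = 0.9: 79.2% (normal 81.2%). Both agree with the stated 80%, so the power statement is sound and is not at issue.

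**2. Does withdrawal on deterioration bias a likelihood-based model?** This was simulated. All settings are assumptions: standardised outcome, five visits from baseline to post, within-person correlation 0.6, control change of -0.3 SD by post, and withdrawal once the rise from baseline exceeds 0.75 or 1.0 SD. There were 200 per arm, to isolate bias from noise, and 100 replicates (simulation standard error about 0.01). The model used categorical time, arm-by-time means and unstructured covariance, fitted by maximum likelihood. Negative values favour CBT.

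| Scenario | Truth -0.8: mixed model | Truth -0.8: completers only | Truth 0: mixed model |
|---|---|---|---|
| Worsening recorded, then withdrawn | -0.80 to -0.81 | -0.70 to -0.71 | 0.00 |
| Withdrawn before recording, both arms | -0.69 to -0.72 | -0.64 to -0.67 | 0.00 to 0.01 |
| Unrecorded in CBT, recorded in control | -0.88 to -0.90 | -0.71 to -0.74 | -0.15 to -0.20 |

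The first row shows no material bias in the mixed model. The second is biased toward zero when there is a true effect. The third favours CBT. The completers-only estimate, which is the form of the EDE analysis, falls short of a true effect of 0.8 in every row. These thresholds removed 12% to 36% of an arm by post, so the table shows direction rather than expected size.

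**3. A simple size calculation.** Let δ be how much worse the withdrawn participants are than the model predicts from their recorded data, in SD. Let pC and pT be the proportions withdrawn with unrecorded worsening in control and CBT. Then bias = δ × (pC − pT). The documents give none of these three inputs; all are assumed.

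- Low end: 1 × (0.10 − 0.04) = 0.06 SD.
- High end: 2 × (0.20 − 0.08) = 0.24 SD.

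With more such withdrawals in control, the bias dilutes the effect. At 23 per arm (two-sample t):

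- No bias, d = 0.80: noncentrality 0.80 × √(23/2) = 2.71, power 75.6%.
- Low end, d = 0.80 − 0.06 = 0.74: noncentrality 2.51, power 69%.
- High end, d = 0.80 − 0.24 = 0.56: noncentrality 1.90, power 46%.

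The baseline for comparison is 75.6%, not 79%: the step from 79.1% to 75.6% is lost sample size. The figure of 23 per arm matches the low-end rates, since 25 × (1 − 0.07) = 23.25, where 7% is the mean of 10% and 4%. At the high-end rates 20 control and 23 CBT participants would remain, and the same calculation gives 72% without bias and 43% with it.

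If the two rates were reversed, the same 0.06-0.24 SD would favour CBT.

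**The case against.** The strongest reply is that the plan already deals with this. The QEWP and weight are taken monthly, and items 10 and 11 expect problems to be picked up through repeated evaluation. Much deterioration may therefore be recorded before anyone is withdrawn, and the mixed model then handles it. The plan also foresees informative dropout and names pattern mixture models. The trial is rated minimal risk, so such withdrawals may be few.

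Much of this stands, and it rules out several stronger readings.

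- A reader might infer that withdrawal for deterioration makes the data missing not at random by definition. It does not. When the worsening is recorded first, missingness depends on observed data, and the simulation shows no material bias.
- A reader might infer that the plan rests on missing at random alone, or that the model gives withdrawn participants the course of those who did well. Neither is so. A sensitivity analysis is named, and the model conditions on each participant's own earlier values.
- A reader might infer a raised false-positive rate in favour of CBT. That needs unrecorded withdrawal to be more frequent in CBT. The contact schedules make this possible, but no document quantifies it. With equal handling in both arms and no true effect, the simulated bias was 0.00 to 0.01.
- A reader might take every such withdrawal to concern eating or weight. The rule speaks of clinical condition, which may cover other problems that need not track either primary outcome.

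The reply does not close the gap. The pattern mixture analysis is conditional on concerns that have no stated criterion, its identifying assumptions are not given, and it would be fitted to about 25 per arm. It cannot recover outcomes that nobody collected. The attrition triggers in item 12 begin at 35%, well above the rates at which the illustration already shows a bias.

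**Conclusion.** The concern holds in this limited form. As written, the rule ends study participation on grounds that overlap both primary outcomes, and no outcome collection is planned afterwards, which sits poorly with the intent-to-treat statement. The mixed-model analyses are at risk to the extent that worsening goes unrecorded before withdrawal, and the direction of bias then depends on the arm in which that happens more. The completers-only EDE analysis is exposed whether or not the worsening was recorded.

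The size cannot be established from the documents. The 0.06-0.24 SD, and the fall in power from 75.6% to between 69% and 46% at 23 per arm, illustrate what would follow if the assumed rates and shifts applied and every counted withdrawal were unrecorded. They are not predictions. The change is worth making because it is cheap and removes the problem at its source. The clinical criterion for withdrawal is not judged here.

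**What to change.** Leave the clinical decision to end treatment and refer exactly as it is. Add to item 10, and repeat in item 13, that this decision does not end outcome collection:

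- The scheduled QEWP, EDE-Q, weight and post-treatment EDE continue unless consent or assent is withdrawn. Weight may be synced, read from a non-smart scale or self-reported, as item 11 already allows.
- A QEWP and a weight are sought at the time of the decision where feasible, and the reason for withdrawal is recorded.
- All these values enter the intent-to-treat analysis.

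It would also help to make the pattern mixture (or a delta-adjusted) sensitivity analysis unconditional, with its assumptions stated in advance.

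The cost is modest: some staff time for follow-up and a matching change to the consent and assent text. Remote participation, home scales and per-assessment payments are already in the protocol. The main drawback is that later values may partly reflect outside care, which should be noted when the results are interpreted.

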Adolescent Treatment. Adolescent therapy (see table) will have five stages and will occur during both the treatment-development and RCT phases of the study: 1) Orienting to treatment and establishing a therapeutic foundation; 2) Specific behavioral strategies and their implementation; 3) Coping skills training and implementation; 4) Integrated executive function skills; and 5) Relapse prevention planning to maintain health behaviors. As in general adolescent therapy (58), parents will have some involvement in therapy but the focus will be on adolescents. Parents will attend sessions monthly, during which they will learn about binge/LOC eating, collaborate to enhance adolescent awareness, identify parent and family factors that could inhibit change, and help the adolescent establish behavioral strategies that maximize improvement. Adolescents will teach parents what they have learned to increase self-efficacy and positive communication. Other developmentally-tailored content includes using tangible therapeutic tools, setting communication strategies and boundaries with parents, eliciting peer support and parent health-behavior support, and focus on both short- and long-term health goals. Executive function techniques will be taught as skills to reduce impulsivity, increase behavioral inhibition, improve planning, and promote long-term benefits in the context of health decision making, as has been done in anorexia nervosa treatment research (59-61). Executive function skills are expected to enhance therapeutic gains from behavioral and coping strategies.

Active Control. The control condition (see table) will address eating behaviors and nutrition, thereby having face validity and broad clinical appeal. The active control will be 4 months with mailed publicly-available information (weekly to match CBT; e.g., USDA healthy recipes, list of local recreation areas and activities) and monthly assessments (parent and adolescent attendance will be matched to CBT).

TABLE 1: CBT for adolescent binge/LOC eating and control conditions

Week	CBT for Adolescents	Control Condition
1	Orient to treatment: Establish collaborative therapeutic relationship with adolescent and parent cooperation; Educate adolescent and parent about binge/LOC eating	Orient to treatment: Establish collaborative relationship with adolescent and parent; Explain program format

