This is a behavioral (NON-medication) RCT that does not involve multiple sites, treatment blinding, or high-risk interventions. Although the pilot RCT does include vulnerable individuals (adolescents 12-17 years old), the risks associated with the proposed pilot RCT, including the cognitive-behavioral treatment and assessment protocols, are judged to pose minimal risks to participants. Therefore, we provide the following plan for monitoring the safety of participants and the integrity and quality of data:

Measurement and Reporting of Data Integrity and Quality

The PI is responsible for monitoring the data, assuring protocol compliance, and conducting the safety reviews. During the review process, the PI will evaluate whether the study should continue unchanged, require modification/amendment, or close to enrollment.

The PI, in consultation with [name] (Primary Mentor), will provide a summary of the DSMP report to the NIH as part of the annual progress report and to the Yale IRB on a yearly basis as part of the annual re-approval process. The DSMP reports will include Subject accrual, Treatment completion rates, Interim analyses, and Adverse and serious adverse events. These reports will be discussed with the mentoring team during regular meetings and sent to the Safety Monitor for review. The frequency of data review is summarized in the following table:

	Data Type	Frequency of Review by PI	Frequency of Review by PI and Safety Monitor
1	Subject accrual	Monthly	Annually
2	Treatment completion rates (retention/attrition)	Quarterly	Annually
3	Interim analyses	Twice Yearly	Annually
4	Adverse and serious adverse event rates	As needed	Annually
5	Checklist for Safety Monitor	NA	Annually

The PI, the Institutional Review Board (IRB) and/or the Safety Monitor have the authority to stop or suspend the study or require modifications.

Subject Accrual

Subject accrual reviews will help to assure that subjects are being enrolled (accrued) at a rate necessary to meet the recruitment goals in general and with regard to racial/ethnic diversity.

Subject accrual rates will be discussed with the PI monthly and annual accrual rates will be reported by the PI to the Safety Monitor to determine if any corrective action is needed to meet the recruitment goals.

Treatment Completion Rates

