Retention, attrition and completion rates will be carefully tracked and reviewed. This will be done quarterly to highlight any possible concerns and will be reviewed formally with the PI and Safety Monitor annually. Differential dropout across treatments and/or higher than expected dropout will be reviewed to determine whether any problems are present and what, if any, corrective action needs to be taken. "Trigger points" for corrective action, as described below, include: 35% ("low alert"), 40% ("mid alert"), 45% ("high alert"), and 50% ("extreme alert"). With early alerts to problems, action

would be taken to avoid higher level alerts; if a higher-level alert should arise, more drastic actions would be taken.

It is possible that baseline differences between the treatment conditions, excessive attrition, and/or missing data will limit the value of the data analysis, and hence knowledge to be gained from this study. For these reasons, interim analyses will be conducted twice yearly. Baseline differences, if present, will be considered in relation to potential effects on the power to detect differences in the primary outcomes. If these effects were to develop and be sizeable, alterations to the randomization schedule would be considered. Such effects would be evaluated and discussed by the PI and mentors, and plans would be communicated to the NIH and Yale IRB. To address excessive attrition and missing data, the following actions would be taken at the “trigger point” for each level of alert:

- 1) Low-level alert (35%): Review of potential problems by PI and review of procedures for supervision of study clinicians.
- 2) Mid-level alert (40%): Meeting between PI and senior study team members to discuss approaches to minimize further dropouts.
- 3) High-level alert (45%): Meeting between PI and senior study team members to determine further alterations to study protocol to complete the study with no further losses.
- 4) Extreme-level alert (50%): In the unlikely event that a 50% dropout rate occurs prior to the mid-study time point, the PI and senior study team members would convene to discuss the usefulness of continuing the study.

It is possible that other situations could occur that might warrant stopping the trial. Any concerns would be discussed with appropriate parties (PI, Mentors, Safety Monitor, NIH, Yale IRB).

Measurement and Reporting of Adverse Events

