Primary Aim 2 is to **test** the acceptability and establish the feasibility of adolescent CBT. Descriptive statistics will quantify clinician/patient treatment ratings, sessions attended, and retention, and clinician adherence/competence through ratings of recorded sessions.

Secondary Aims.

Secondary Aim 1 is to **explore** the efficacy of adolescent CBT relative to active control: (a) reduction in disordered eating thoughts and behaviors (EDE-Q), (b) improvements in executive function (S-Upps, Kirby), (c) improvement in psychosocial functioning (reduced depression, PHQ; improved self-esteem, RSES).

Secondary Aim 2 is to **explore** the durability and maintenance of treatment effects during short-term follow-up.

Secondary Aim 3 is to **explore** potential predictors of primary outcomes. Following Kraemer's (109) conceptual/statistical model for predictors, we will explore whether baseline characteristics predict treatment effects by testing for main effects and interactions in models for primary outcomes (specified above), including (a) adolescent executive function (S-Upps, Kirby), (b) self-weighing (EARLY), (c) parent BMI and disordered eating behaviors (EDE-Q/QEWP), and (d) parent feeding practices and attitudes (CFQ). [name] et al (25) used this analytic strategy in earlier work.

Power Analysis and Justification of Sample Size. Results are anticipated to yield significant impact by providing effect sizes for grant applications to perform definitive studies comparing the new adolescent CBT treatment with existing interpersonal therapy for youth LOC. Power estimates for the pilot RCT were based on the comparison of CBT (n=25) and control conditions (n=25). Assuming a two-sided test at $\alpha=0.05$ threshold, we have 80% power to detect clinically meaningful between-subjects ($d=0.8$) and within-subject effects within each group ($d'=0.58$). Even assuming 20% dropout, we still have 80% power to detect clinically meaningful effects ($d=0.9$ between-subjects and $d'=0.66$ within-subject). While power is limited given the pilot nature of the study, such effects are similar to effects observed in a prior study (31) that compared LOC eating between youth who received either interpersonal therapy or were in a control group. Thus, we have a reasonable chance of finding statistically significant differences between CBT and control, even in this pilot study.

SECTION II: RESEARCH INVOLVING DRUGS, BIOLOGICS, RADIOTRACERS, PLACEBOS AND DEVICES
--

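### Do the 35–50% dropout alerts and the Primary Aim 2 retention figure need a counting rule fixed in advance?

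*Combined protocol and SAP*

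**What the plan says.** Section I, item 12 (Data and Safety Monitoring Plan) lists "Treatment completion rates (retention/attrition)" among the data types in its review table, seen quarterly by the principal investigator and annually with the Safety Monitor. Under Treatment Completion Rates it adds that "Retention, attrition and completion rates will be carefully tracked and reviewed" and that "Differential dropout across treatments and/or higher than expected dropout will be reviewed to determine whether any problems are present". Four alert levels follow (35, 40, 45 and 50%), introduced as the response to both attrition and missing data. Their actions run from a review of procedures, through two levels of team meeting, to a discussion of whether continuing is useful. Only the 50% level has a time limit, the middle of the study, and that point is not defined.

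Item 13 (Statistical Considerations) uses the same vocabulary for other purposes:

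- Baseline section: "Dropouts and completers will also be compared".
- Primary Aim 1, on the EDE interview: "because this interview is only administered at baseline and post, this analysis will, by definition, occur among completers".
- Primary Aim 2: "Descriptive statistics will quantify clinician/patient treatment ratings, sessions attended, and retention".
- Power: "Even assuming 20% dropout, we still have 80% power to detect clinically meaningful effects", with d = 0.9 between groups and d' = 0.66 within group.

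On the control arm, item 4 says: "The active control will be 4 months with mailed publicly-available information". The same sentence adds monthly assessments, with parent and adolescent attendance matched to CBT.

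**The concern.** A percentage that triggers an action should have a stated numerator and denominator. Here the review table points to finishing treatment, the EDE sentence points to having a post interview, and the power paragraph treats a dropout as a lost outcome. These can differ for one person. Analyses are intent-to-treat and assessments are paid for separately (Section VI, item 2), so an adolescent can stop sessions and still be assessed at post. They can also differ by arm, because CBT has 16 weekly sessions and the control arm has mailings plus monthly assessments.

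If the rule were settled only after the data were seen, four things could shift: whether an alert level counts as reached, the review of differential dropout, the membership of the dropout and completer groups, and the retention figure. The last matters most, since acceptability and feasibility form a primary aim of this pilot.

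**Working it through.** **1. The plan's own figures.** Inputs from the power paragraph in item 13: 25 per arm, two-sided α = 0.05, 80% power, 20% dropout. Then 25 × (1 − 0.20) = 20 per arm. Noncentral t calculations give:

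| Comparison | n | Stated effect | Power at stated effect | Effect detectable at 80% |
|---|---|---|---|---|
| Between groups | 25 per arm | 0.8 | 0.791 | 0.809 |
| Between groups | 20 per arm | 0.9 | 0.792 | 0.909 |
| Within group | 25 | 0.58 | 0.795 | 0.584 |
| Within group | 20 | 0.66 | 0.799 | 0.660 |

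All four reproduce to rounding. The 20% is the usual reduction of the sample for a sensitivity case. It is neither a planned rate nor a definition of dropout.

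**2. Can the choice of rule move the percentage?** Assumed counts, not from the documents: of 25 CBT participants, 10 stop sessions and 6 of those 10 still give a post assessment; of 25 controls, 3 lack post.

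- CBT arm, stopped sessions: 10/25 = 40%, the second alert level.
- Pooled, stopped sessions (CBT) or lacking post (control): (10 + 3)/50 = 26%, no alert.
- Pooled, lacking post: (4 + 3)/50 = 14%, no alert.
- CBT retention: 15/25 = 60% by sessions, or 21/25 = 84% by post assessment.

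So the choice can matter to the label attached to the same data.

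**3. Is there one rule that is plainly better?** The 35% level needs ceil(0.35 × 25) = 9 in one arm, or ceil(0.35 × 50) = 18 pooled. With assumed true dropout of 40% in CBT and 20% in control:

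- P(Binomial(25, 0.40) ≥ 9) = 0.726.
- P(Binomial(25, 0.40) + Binomial(25, 0.20) ≥ 18) = 0.212.

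Pooling steadies the rate but hides a one-arm problem. Counting only missed post assessments gives an objective event with the same meaning in both arms, but it waits until month 4, and item 12 wants early warning. Reading percentages on few participants has the opposite fault: at a true rate of 20%, the 50% level is reached with probability P(X ≥ 2 of 4) = 0.181, against P(X ≥ 10 of 20) = 0.003. Each rule gives something up.

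**4. What does the rule touch?**

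| Use of the term | Effect of the missing rule |
|---|---|
| QEWP and BMI z-score mixed models | None: all enrolled participants and all available observations enter |
| EDE analysis | None: its set is fixed by having both interviews |
| Alert levels | Timing of a review or meeting; no automatic stop |
| Dropout and completer comparison | Group labels in a supportive table |
| Primary Aim 2 retention | A descriptive percentage, with sessions attended listed separately |

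**The case for a change.** The strongest case for a change is that it would cost a few sentences, and that the same data can read as no alert or as the second level. Retention belongs to a primary aim, the 45% level contemplates altering the protocol, and the 50% level opens the question of continuing. Routine quarterly review does not help if nobody has said what is being counted.

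Part of this stands. No section supplies the counting rule, the study midpoint is undefined, and the review table's label sits awkwardly beside the later uses of the same words.

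The rest is weaker than it looks. The alert levels are introduced as a response to attrition and missing data together, and their wording concerns losses from the study, so the intended quantity is reasonably clear. The treatment-completion sense rests on a table label and the heading that repeats it. The arms do differ in sessions, but they share one assessment schedule and attendance is matched, so assessment attendance gives a common unit for comparing them. Items 4 and 13 already keep sessions attended apart from retention, so a reader of the results would see both. A rule written now would also have to choose between sensitivity and stability, and the 0.73 against 0.21 shows that choosing the pooled rate would weaken the warning in the example that causes the worry.

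**Conclusion.** The observation is correct but calls for no change. It is missing operational detail that analysts fill sensibly by showing, for each arm, the number randomised, the number due at each assessment, the number assessed, and the sessions attended in CBT. With those counts any reader can form the rate they prefer, and the 60% and 84% in the illustration would both be visible.

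The size is limited. In the assumed example the reading moves the dropout rate between 14% and 40%, but no stated figure is wrong, neither primary comparison changes, and the most an alert does is bring a review or meeting forward or push it back.

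This rests on three conditions, all consistent with the text: the alerts remain prompts for judgement and not statistical stopping rules, the primary models keep every enrolled participant, and the retention percentage is published with its numerator and denominator. The example counts and the 40% and 20% rates are assumptions chosen to show the mechanism; the documents give no expected dropout rate for either arm.
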